**SUMMARY OF CHANGES**

Revision Level	Description of Changes	Date
1.0	Initial Release	June 11, 2019

**Protocol Summary**

Device	Personal KinetiGraph® (PKG®) System						
Control	Clinic Standard of Care						
Study Objective	
This is a randomized controlled trial (RCT) to evaluate treating uncontrolled patients with Parkinson’s Disease (PwP) to a target range established by a published expert opinion manuscript. The study aims to evaluate clinical patient outcomes, quality of life measures and health care utilization of those patients specifically treated to a target range when using the PKG data in the clinical management of Parkinson’s disease (PD) in routine clinical care (treatment group) compared to those managed with medical history and clinical evaluation alone (control group) performed by a neurologist experienced in PD management. Both groups will be recommended to undergo medication changes until they reach a “controlled state” that is determined by either the clinician using standard of care (SOC) (PKG- Group) or using PKG based targets and SOC assessments (PKG+ Group). For subjects in the treatment arm (PKG+ Group) the references will be according to the following table using PKG scores* :
 
  
 	Target Range	
   
 Bradykinesia Score (BKS)	Median BKS 23-25 and/or FDS > 7.5	
 
 Dyskinesia Score (DKS)	Median DKS 7-9 and FDS < 13	
  
 
The main objective of this study is to evaluate whether PwP who are managed with the aid of objective measurement and use of target ranges have improved PD symptoms and outcomes as compared to individuals treated using only standard of care (medical history, neurological examination).
		Target Range	Bradykinesia Score (BKS)	Median BKS 23-25 and/or FDS > 7.5	Dyskinesia Score (DKS)	Median DKS 7-9 and FDS < 13
	Target Range						
Bradykinesia Score (BKS)	Median BKS 23-25 and/or FDS > 7.5						
Dyskinesia Score (DKS)	Median DKS 7-9 and FDS < 13						
Study Design	Prospective, multi-center, single-blind randomized (1:1) controlled, longitudinal follow-up study (1, 2, 3 years)						
Number of Subjects	Up to 350 randomized subjects total (approximately 175 in each arm)						
Number of Sites	Up to 40 Centers in the U.S. comprised of Movement Disorder Specialists (MDS) and General Neurologists (GN) experienced in PD management.						
Primary Endpoint	The change in MDS-UPDRS Total score at 4 months from baseline defined as sections I, II, III and IV in PwP. The endpoint will be compared between those who						

**TARGET-PD**

	
are treated with standard of care and PKG data (PKG+ Group) and those who are treated per standard of care alone (PKG- Group).
 
Subjects will be assessed in the ON state.

Secondary Endpoints	
Secondary endpoints will include measurements as indicated below:
 
 
● Percent “responders” for MDS-UPDRS Total score (based on a minimum clinically important change of >4 points)**
 
● Change in motor endpoints at 4 months, 1, 2, 3, years including:             
 
○ MDS-UPDRS Part III;
 
○ PKG Bradykinesia score (BKS),
 
○ PKG Dyskinesia score (DKS) and measurement of OFF time
 
 
 
● Change in PDQ-39 from baseline to 4 months, 1, 2, 3 years
 
● Change in MDS-UPDRS Total score from baseline to 1, 2, 3 years
 
● Change in MDS-UPDRS Parts I from baseline to 4 months, 1, 2, 3, years
 
● Change in MDS-UPDRS Parts II from baseline to 4 months, 1, 2, 3, years
 
● Change in MDS-UPDRS Part IV from baseline to 4 months, 1, 2, 3, years
 
● Change in PKG Scores including BKS, DKS, PTT, FDS and PTI from baseline to 4 months, 1, 2, 3 years
 
● Change in Levodopa Equivalent Dose (LED) from baseline to each interim visit and 4 months, 1, 2, 3 years
 
● PKG Patient Survey at 4 months, 1, 2, 3, years
 
 
Subjects will be assessed in the ON state as applicable.

Ancillary Endpoints	
Ancillary endpoints will include measurements as indicated below:
 
 
● Rate of protocol defined adverse events affecting health care utilization including: hospitalizations, emergency department, urgent care or unanticipated clinic visits from baseline to 4 months, 1, 2, 3 years follow-up
 
● Rate of protocol defined adverse events and potential contraindications for increasing dopaminergic therapy including: falls, orthostatic hypotension, bothersome hallucinations, delirium, and impairment that prohibits interaction with the PKG watch from baseline to 4 months, 1, 2, 3 years follow up
 
● Rate of enrolled subjects in PKG+ Group who are unable to be brought into Target Range throughout follow-up period
 

Study Population	Patients with Parkinson’s Disease
Inclusion Criteria	
Study subjects must fulfill the following criteria:
 
 
● Able and willing to sign a written informed consent for study participation
 
● Presumed to have Levodopa responsive idiopathic Parkinson’s Disease
 
● Age inclusive at the time of consent per PKG Indications for Use (46-83 years old)
 

**TARGET-PD**

	
 
• Has not been previously managed with the PKG
 

Exclusion Criteria	
Subject with any of the following clinical criteria should be excluded:
 
 
• Contraindication to increasing levodopa (e.g. orthostatic hypotension, hallucinations/psychosis or any other medical condition in the last year that would preclude increasing levodopa or other appropriate Parkinson’s Disease medications)
 
• MoCA score <23 at screening visit
 
• Diagnosis of Essential Tremor
 
• Wheelchair bound or bedridden
 
• Currently utilizing or planning in the next 6 months advanced PD therapies (DBS, infusion, etc.)
 
• In the investigator’s or sponsor’s opinion, subject has any unstable or clinically significant condition that would impair the participant’s ability to comply with study requirements or interfere with interpretation of the study endpoints (e.g., subject unable to complete PKG watch wear instructions per Patient Instruction Manual)
 
 
Subjects will be assessed in the ON state where applicable.

Statistical Methods	
The primary endpoint of change in total MDS-UPDRS will be compared between the treatment group (PKG+ Group) and the control group (PKG- Group) based on a two-sample t-test. In the event normality assumptions are violated, a non-parametric analog will be used. A difference between groups of 5 points is assumed for the change in total MDS-UPDRS as well as a standard deviation of 13 based on historical data. With these assumptions, a sample size of 280 evaluable subjects will provide approximately 83% power for the statistical hypothesis test for the primary endpoint. To account for attrition of up to 20%, a total enrollment of 350 subjects is planned.
 
The primary analysis will be based on the intent-to-treat (ITT) population defined as all randomized subjects analyzed according to the treatment group assigned. Except where otherwise specified, the following general principles apply to the planned statistical analyses. All statistical analyses will be conducted using SAS version 9.4 or later (SAS Institute Inc., Cary, NC) or other widely-accepted statistical or graphical software as required. Continuous variables will be summarized with mean, standard deviation, median, max, min, and number of evaluable observations. Categorical variables will be summarized with frequency and percentages. Confidence intervals may be presented where appropriate using the t-distribution for continuous variables and Clopper-Pearson Exact method for categorical variables. Unless otherwise specified, statistical analyses will be performed using a one-sided 0.025 alpha level.

**TARGET-PD**

Study Visits	
 
• Screening
 
• Baseline (28 days +/- 7 days)
 
• Interim Visits (within approximately 21-35 days of previous visit)– investigators will be recommended to change medications until the patient is within the defined target range (PKG+ Group) or per investigator SOC assessments (PKG- Group); up to 3 interim visits allowed
 
• 4 months follow-up (120 days +/- 30 days)
 
• 1 year follow-up (12 months +/- 2 months)
 
• 2 year follow-up (24 months +/- 2 months)
 
• 3 year follow-up (36 months +/- 2 months)
 

---------------------	--

## 1.0 Introduction

### *Importance of motor management in Parkinson's Disease*

Parkinson's disease is a progressive disease of the nervous system marked by tremor, muscular rigidity, and slow, imprecise movement, chiefly affecting middle-aged and elderly people. These symptoms are associated with degeneration of the basal ganglia in the brain and a deficiency of the neurotransmitter dopamine. Parkinsonism refers to the collective clinical symptoms of bradykinesia, rigidity, resting tremor, and postural and gait impairments. Accumulation of alpha-synuclein in the brain is a typical neuropathological hallmark of Parkinson's disease occurring early in the course of the disease and may predate the appearance of clinical features of the disease. Manifestations in the autonomic system controlling certain functions like heart rate, digestion, etc. may also precede motor deficits of the disease. Disease progression has been shown to be attributed to alpha-synuclein spreading from diseased to healthy cells. Individuals with Parkinson's may exhibit diverse symptoms including behavioral, autonomic, somatic, and cognitive deficits however motor impairment, specifically bradykinesia or slowed movement, is required for diagnosis.

Motor symptoms are secondary to the continued loss of dopaminergic neurons in the par compacta of the substantia nigra. Upon treatment with dopaminergic therapies, individuals may develop iatrogenic motor complications that may be controlled through adjustment of medications. Approximately 40% of patients develop fluctuations and dyskinesia within 4-6 years of treatment and 70% after long-term treatment (>9 years). Patients with fluctuations tend to have greater disease severity and disability, and those that fail to derive adequate benefit from medications report poorer quality of life. Signs and symptoms of fluctuations vary, and it is thought that they may be under-recognized by clinicians as direct observation is often impractical and patient symptom recall can be incomplete and unreliable.

Other symptoms may impact PD patients through the disease progression. Tremor is present in about 60-70% of subjects with the typical resting tremor being helpful in differentiating PD from other forms of parkinsonism. Additionally, approximately 90% of patients with PD will develop at least one nonmotor symptom, and nonmotor symptoms can be the presenting feature in PD.

### *Justification for use of objective targets in the management of Parkinson's disease*

Treating Parkinson's disease is challenging because of fluctuations in symptoms from day to day and throughout the course of a day. Other symptoms can also impact the variability of PD on an ongoing basis. Currently, in routine practice, most clinicians rely on clinical evaluation, a patient's self-reporting of symptoms and response to medication, to guide therapy. Clinical evaluations may be in the form of an unstructured interview or semi-structured questionnaires, that vary from provider to provider in terms of content, depth, and scope, or formal clinical assessment tools such as the Unified Parkinson's Disease Rating System (UPDRS). Some clinicians employ the use of subject symptom diaries. There are well-known limitations with

**TARGET-PD**

these assessment methods including: no assessment during activities of daily living, poor visibility of compliance with medications, inadequate recall and/or reporting of symptoms, no or poor data quality control and inter-rater variability.

Wearable technologies have been developed in response to the lack of objective measurement tools for movement disorders symptoms and are being used in the clinical care of Parkinson's patients. Recent studies have suggested that the use of wearable sensors can inform medication choices in a clinical trial setting and correlate with relevant clinical assessment scales.

A recent study by Farzanehfar, *et al.* demonstrated that the use of objective targets and measurement with the PKG® system significantly improved clinical care and quality of life for people with PD. For the first time, this study provided clinicians with objective and continuous information to help calibrate their treatment recommendations in a timely method. The study included 103 PD patients from the Northern part of Tasmania, Australia, with low levels of access to specialist care.

Key findings of this study included:

- Most people with PD (78%) were living with excessive symptoms that were out of target, including high levels of bradykinesia (slowness and freezing), dyskinesia (involuntary movements) and tremor (constant shaking).
- With the use of objective measurements and targets reported with the PKG® system, management was improved in more than half (58%) of the 77 participants who completed the study.
- Most significantly, PKG monitoring and use of targets led to changes in oral medication, which improved quality of life and clinical outcomes of 43% of patients who completed the study (33 patients):
  - 10-point improvement in quality of life as assessed by the PD Questionnaire (PDQ-39) ( $p < 0.08$ ).
  - 8-point improvement in clinical symptoms as measured by Total UPDRS clinical scale ( $p < 0.0009$ ).

Additionally, in 2018, two panels of movement disorder specialists published expert opinion manuscripts that serve as a basis for objective measurement to be incorporated into clinical practice guidelines. Both expert groups developed treatment targets for the management of bradykinesia, dyskinesia and motor fluctuations. These therapeutic targets will be evaluated in this study.

*Personal KinetiGraph (PKG®) Movement Recording System*

The Personal KinetiGraph (PKG®) Movement Recording System was developed by neurologists at the Melbourne-based Florey Institute of Neuroscience and Mental Health. The product is manufactured and marketed by GKC.

The Personal KinetiGraph (PKG®) Movement Recording System consists of the following:

- A wrist-worn data logger (PKG Watch) designed to acquire data on the kinematics of movement disorder symptoms over a 6-10 day period.
- An application to configure the data logger and transfer the acquired data at the end of a recording.
- A series of algorithms that analyze the uploaded data, producing a PDF that is delivered to the clinician. The PDF contains objective data distinguishing the movement patterns consistent with tremor, bradykinesia, dyskinesia and immobility.
- Supporting device accessories.

## 2.0 PKG System

### PKG Watch

The PKG Watch is a wrist worn medical device that looks like a wristwatch. It is worn on the wrist of the most severely affected side and contains a rechargeable battery, a triaxial accelerometer, memory, an optional vibration and indicator light-based reminder to the subject when PD medications are due and a means for recording when Parkinson's disease (PD) medications were taken, as well as a capacitive sensor to detect removal from the wrist.

Subjects wear the device for 6-10 consecutive days. During this wear time the PKG Watch automatically collects data on the type of movement experienced by the patient 24 hours per day, can remind the patient to register when they have taken their PD medication as prescribed by their clinician, and the patient can indicate when he/she has taken each prescribed dose of PD medication.

At the end of the recording period, data are downloaded and analyzed using a proprietary algorithm to translate raw movement data collected by the PKG Watch into a multi-page, printable output of the patient's movement over the wear period. This output is called a "PKG." The maximum acceleration in each 2-minute epoch is identified and the mean spectral power surrounding this peak is calculated. Algorithms produce Bradykinesia Scores (BKS) and Dyskinesia Scores (DKS) every two minutes. The PKG includes:

- a scaled record of a dyskinesia score (DKS) representative of dyskinesia plotted against time of day for individual days over the full recording period (Figure 2).
- a scaled record of a bradykinesia score (BKS) representative of bradykinesia plotted against time of day for individual days over the full recording period (Figure 2).
- a record of periods of immobility, which may be indicative of periods of daytime sleep and somnolence, plotted against time of day.

- a record of periods when the patient was not wearing the PKG Watch or when it was 'off-wrist'.
- a record of the patient's self-reported compliance with their prescribed program of Parkinson's disease medication.
- a record of periods of tremor for each day and a tremor summary.

Dyskinesia + Bradykinesia Daytime Session Averages

[figure not shown]

Figure 1: PKG Main Plot

2.1 Clinical Interpretation

Bradykinesia Scores (BKS) and Dyskinesia Scores (DKS) are continuous variables. In the case of the BKS, the scores can range from movements that are made with normal acceleration to those that have very low or no acceleration. There is a correlation between the median BKS and DKS between 0900-1800 hour and clinical rating scales.

A very high bradykinesia score represents complete immobility of the logger for that 2-minute period. These periods of immobility had a 85.2% concordance with the detection of sleep by ambulatory daytime polysomnography, ( $p < 0.0001$  Chi Squared). High Epworth Sleepiness Scores (ESS) were associated with a high proportion of time immobile (PTI) throughout the day ( $p > 0.01$  Mann-Whitney). The median PTI between 0900 -1800 hours in 30 age matched control subjects was 2%, representing 10 min. PD patients had higher PTI (median 4.8%) than controls ( $p < 0.0001$ , Mann-Whitney). PD subjects with a PTI above the 75th percentile (5% or 27 min) of controls had more bradykinesia, less dyskinesia and higher PDQ-39 scores than those with PTI below this level. There was no relationship between PTI and dose or type of PD

medications. However, in 53% of subjects, PTI increased in the 30-60 min after levodopa confirming that in some subject's levodopa results in increased sleepiness.

The PKG Watch can deliver a reminder to take PD medication by delivering a vibratory cue to the wrist. Consumption of medications is acknowledged by the subject. Some patients performed this acknowledgement repeatedly and unconsciously and this behavior is a risk marker for Impulse Control Disorder. A Response Ratio (RR) represents the number of acknowledgements/ number of doses and is expressed as a percentage. In ~75% of people with PD who had high Impulsive-Compulsive Behavior (ICB) Scores, the RR was tightly correlated with ratings of Impulsive-Compulsive Behaviors ( $r^2=0.79$ ). These patients had dyskinesia, particularly when making extraneous responses. In the other 25% who had high Impulsive-Compulsive Behavior Scores according to rating scales, the RR was low and these subjects had higher Apathy scores and low levels of dyskinesia. It was concluded that the elevated Response Ratio is a specific measure of a type of Impulse Control behavior where increased incentive salience is attributed to cues by the presence of high striatal dopamine levels, manifest by high levels of dyskinesia and that there is a second form of ICBs which occur in the absence of dyskinesia, has normal Response Ratios and higher Apathy scores and may represent prefrontal pathology.

A Fluctuation Dyskinesia Score (FDS) was produced from the PKG data by summing the interquartile range of bradykinesia scores and dyskinesia scores and expressing it as an algorithm. This FDS can distinguish between fluctuating and non-fluctuating patients with high sensitivity and selectivity and was significantly lower following activation of deep brain stimulators. The FDS following deep brain stimulation lay in a band just above the score separating fluctuators from non-fluctuators, suggesting a range representing adequate motor control. When compared with control subjects the FDS of newly diagnosed patients show a loss of fluctuation with onset of PD. The FDS was calculated in subjects whose duration of disease was known and this showed that newly diagnosed patients soon develop higher scores which either fall under or within the range representing adequate motor control or instead go on to develop more severe fluctuations. It was concluded that the FDS promises to be a useful tool for identifying patients whose fluctuations are progressing and may require therapeutic changes.

## 2.2 PKG and PKG Report

The investigator will be provided a summary report of the PKG that includes key findings by an independent neurologist, registered nurse and/or neuro diagnostic technologist trained specifically in interpreting the PKG for the PKG+ Group only. It is intended that the investigator then reviews and assesses the PKG information and additionally reviews findings with the patient, concluding the likely impact of the disease on the movement of the patient. This PKG and PKG report may lead the clinician to prescribe a change in medication amount/frequency or recommend a new therapy until the patient becomes controlled.

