## 4.0 Methods

### 4.1 Study Design Overview

The TARGET-PD RCT investigates the use of the PKG and standard of care in treating towards a target range compared to standard of care alone in the treatment of patients with uncontrolled Parkinson's disease. This is a prospective, multi-center, single-blind, randomized controlled study.

Each subject will be followed for 4 months after the baseline visit. All subjects in either group will have interim visits until they are considered to be controlled by the clinician per SOC (PKG-Group) or in the PKG based target range (i.e., controlled per expert review paper guidance in Pahwa et al., 2018) for the PKG+ Group. Interim visits may be conducted via telephone or in-office.

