#### 4.4 Baseline Visit

At 28 days +/- 7 days (21-35 days) after the screening visit, subjects will return to the clinic for the Baseline Visit. For the PKG+ Group, the site staff will ensure the PKG Report is available prior to the Baseline Visit. A subject unable to wear a PKG Watch for at least 6 full days may be exited from the study (complete Study Completion Form) if they are unable to complete a repeat wear of the PKG Watch.

Subjects in both groups will undergo the routine clinical evaluation per standard of care. For all subjects, a medical history update, medication history, and an "ON" state neurological assessment will be completed. Protocol defined adverse events including falls, orthostatic hypotension, bothersome hallucinations, delirium, impairment that prohibits interaction with the PKG watch will be recorded. All subjects will also complete the PDQ-39 questionnaire and MDS-UPDRS. If the MDS-UPDRS is not considered part of the routine clinic visit, the MDS-UPDRS will be conducted for all visits by an independent certified rater.

For subjects in the PKG- Group (SOC control group), protocol required data collection will occur at the baseline visit. A Subject "ON" State Assessment will be completed and changes in medical history and medications will be recorded. The study investigator will complete the Clinician Assessment CRF to denote patient-reported symptoms, treatable findings, and clinical management planning based on his/her routine clinical assessment procedures. The study investigator will be blinded to the PKG information. In this group, the investigator will use clinical history and examination to determine if the subject is "controlled" or "uncontrolled" based on standard of care.

For subjects in the PKG+ Group, the study investigator will review and report on the PKG prior to the visit and use the information to guide the discussion with the subject during the clinical assessment. Subjects will remain blinded to their treatment group so direct reference to the PKG is to be avoided. The PKG will be used to determine if the subject is "controlled" or "uncontrolled" using the consensus-derived target ranges. PKG results will be recorded in the PKG Reporting CRF. The study investigator will complete the Clinician Assessment CRF to denote patient-reported symptoms, treatable findings, and clinical management planning based on his/her routine clinical assessment procedures along with the PKG information.

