#### 4.5 Interim Follow-Up Visits

Interim follow-ups will be completed for subjects who are not considered to be controlled. For PKG- group subjects, controlled means per clinician standard of care assessment and for PKG+ group subjects, this is per the Acceptable Target Range:

	Target Range
Bradykinesia Score (BKS)	Median BKS 23-25 and/or FDS > 7.5
Dyskinesia Score (DKS)	Median DKS 7-9 and FDS < 13

Interim visits can be completed in-clinic or remotely via telephone per institutional requirements. This timeframe may vary depending on a variety of factors such as physician care practices, amount of total medication change needed, subject medication regimen compliance and subject tolerance to medication changes.

Approximately 28 days prior to each planned subject follow-up visit, a PKG Watch will be ordered through the GKC Portal and dispensed to each subject as previously described and PKG report obtained prior to the visit of PKG+ group subjects for investigator review.

For subjects in the PKG+ Group, the site staff will ensure the PKG is available prior to the Interim Follow-up Visit. Protocol required data collection will occur at each follow-up interim visit. A Subject "ON" State Assessment will be completed and changes in medical history and medications will be recorded. Any protocol defined AEs that have occurred will be captured on the AE Reporting CRF (see Section 8). The study investigator will review the PKG provided by GKC prior to the visit and use the information to guide the discussion with the subject during the clinical assessment. PKG results will be recorded in the PKG Reporting CRF. The study investigator will complete the Clinician Assessment CRF to denote patient-reported symptoms, treatable findings, and clinical management planning based on his/her routine clinical assessment procedures along with the PKG information.

For subjects in the PKG- Group, protocol required data collection will occur at each follow-up interim visit. A Subject "ON" State Assessment will be completed and changes in medical history and medications will be recorded. The study investigator will complete the Clinician Assessment CRF to denote patient-reported symptoms, treatable findings, and clinical management planning based on his/her routine clinical assessment procedures. The study investigator will be blinded to the PKG information during interim visits.

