#### **4.6 4-Month Follow-Up Visit**

All subjects will complete a follow-up visit approximately 4-months +/- 30 days (90-150 days) from the Baseline Visit.

Approximately 28 days prior to each planned subject follow-up, a PKG Watch will be ordered through the GKC Portal and dispensed to each subject as previously described. The site staff will ensure the PKG is available prior to the visit for the PKG+ Group.

Subjects in both groups will undergo the routine clinical work-up per standard of care. Protocol required data collection will occur at the visit. A Subject “ON” State Assessment will be completed and changes in medical history and medications will be recorded. Any protocol defined AEs that have occurred will be captured on the AE Reporting CRF (see Section 8). Subject surveys will be administered and include the PKG Patient Survey, PDQ-39, MDS-UPDRS, and MoCA. Medication changes (PD and other) will be updated in the corresponding medication log in the CRF.

For subjects in the PKG- Group (control group), the study investigator will complete the Clinician Assessment CRF to denote patient-reported symptoms, treatable findings, and clinical management planning based on his/her routine clinical assessment procedures. The study investigator will be blinded to the PKG information. In this group, the investigator will use clinical history and examination to determine if the subject is “controlled” or “uncontrolled.”

For the PKG+ Group, the site staff will ensure the PKG Report is available prior to the 4-Month Follow-Up Visit. A subject unable to wear a PKG Watch for at least 6 full days may be exited from the study (complete Study Completion Form) if they are unable to complete a repeat wear of the PKG Watch. The study investigator will review and report on the PKG prior to the visit and use the information to guide the discussion with the subject during the clinical assessment. The PKG will be used to determine if the subject is “controlled” or “uncontrolled.” PKG results will be recorded in the PKG Reporting CRF. The study investigator will complete the Clinician Assessment CRF to denote patient-reported symptoms, treatable findings, and clinical

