4.3. Blinding

The subject will be blinded to the randomization assignment throughout the follow-up phase. For the PKG- group, both the subject and the study staff will remain blinded to the PKG scores throughout the study.

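### Protocol 2.2 has PKG findings reviewed with PKG+ patients without the limit that 4.4 sets to protect the subject's blind, and 4.5 to 4.7 do not repeat that limit

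*Protocol*

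**What the plan says.** Protocol 4.1 describes the design in these words: "This is a prospective, multi-center, single-blind, randomized controlled study". Two places say that the subject is the masked party. Protocol 4.4, on the Baseline Visit, says "Subjects will remain blinded to their treatment group so direct reference to the PKG is to be avoided". SAP 4.3 says "The subject will be blinded to the randomization assignment throughout the follow-up phase".

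Protocol 2.2 describes how the PKG report is used. The summary is prepared by staff "trained specifically in interpreting the PKG for the PKG+ Group only". The investigator then studies the PKG output and "additionally reviews findings with the patient". The sentence before this speaks of the report's key findings, so the findings meant are those of the PKG.

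For later visits the protocol describes the PKG+ consultation in nearly the same way each time. Section 4.5 reads: "The study investigator will review the PKG provided by GKC prior to the visit and use the information to guide the discussion with the subject". Sections 4.6 and 4.7 carry equivalent instructions.

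**The concern.** Only the PKG+ arm has a report for the investigator to use. A subject whose investigator goes through PKG findings with them can therefore work out the arm. An investigator who follows 2.2 as written, without the limit found in 4.4, would undo the masking that 4.4 and SAP 4.3 claim.

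This matters because no other masking to arm is stated. The PKG+ investigator holds the report and so knows the arm. In the PKG- arm, staff are blinded to PKG scores, which is not the same as being blinded to assignment. Section 4.4 requires an independent certified MDS-UPDRS rater only where the scale is not part of the routine visit, and does not say that this rater is masked.

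The outcomes exposed are the self-reported PDQ-39, a secondary endpoint, and whatever parts of the MDS-UPDRS the subject answers. The MDS-UPDRS total is the primary endpoint, and Protocol 4.6 lists the scale among the subject surveys. A subject who knows that treatment was steered by a device may report differently for that reason alone.

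**Working it through.** No figure in either document bears on this point, so the check is a comparison of the texts.

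| Place | PKG+ investigator and subject | Limit on mentioning the PKG? |
|---|---|---|
| Protocol 2.2 | Reviews findings with the patient | None |
| Protocol 4.4 (Baseline) | PKG guides the discussion | Yes: no direct reference |
| Protocol 4.5 (Interim) | PKG guides the discussion | None |
| Protocol 4.6 (4-Month) | PKG guides the discussion | None |
| Protocol 4.7 (Annual) | PKG guides the discussion | None |
| SAP 4.3 | Not described | None; says only that the subject is blinded to assignment throughout follow-up |

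1. *Does 2.2 point to the limit in 4.4?* No. It has neither a qualifier nor a cross-reference.

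2. *Can 2.2 and 4.4 be reconciled?* Yes, if 2.2 is read as subject to 4.4: the investigator discusses symptoms and movement and does not name the source. The reader has to supply that reading.

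3. *Does the limit carry forward?* Not explicitly. In 4.4 the instruction to let the PKG guide the discussion and the rule against naming it stand together. In 4.5, 4.6 and 4.7 the first appears without the second. The rule is therefore missing from the section for the visit at which the primary endpoint is measured.

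4. *How long must the blind last?* SAP 4.3 says throughout the follow-up phase. Protocol 5.2 has PDQ-39 and MDS-UPDRS endpoints at 1, 2 and 3 years as well as at 4 months. The SAP analyses only through 4 months.

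5. *Does anything else in the design reveal the arm?* Not in itself. Under Protocol 4.2 both arms wear the watch with the same programming, and both complete the PKG Patient Survey. The route to unblinding is the discussion of findings.

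6. *Which visits can new wording still reach?* The SAP gives 27 February 2020 as the close of enrollment. Adding the longest windows, 35 days to Baseline and 150 days from Baseline to the 4-month visit, gives 35 + 150 = 185 days, or 30 August 2020. The SAP took effect on 9 September 2020. If the windows held, every 4-month visit was over by then, and new wording could affect only the annual visits.

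**The case against.** The strongest answer is that 2.2 belongs to the device description and states an intention, while 4.4 is the operative procedure and supplies the missing limit. Subjects are blinded to their group and not to their clinical state, so findings can be discussed without saying where they came from. This stands in part. It defeats the reading that the two sections cannot both be followed. It does not explain why the limit appears for one visit only, nor does it put the limit into 2.2.

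Four stronger readings are tempting, and the documents do not support them.

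- A reader might infer that SAP 4.3 also forbids mention of the PKG. It does not. It says that the subject is blinded to assignment; only Protocol 4.4 bars direct reference.
- A reader might infer from Protocol 4.6 that the PKG Patient Survey prompts subjects to think about their arm just before the outcome ratings, because the text runs "Subject surveys will be administered and include the PKG Patient Survey, PDQ-39, MDS-UPDRS, and MoCA". That is a list of contents and sets no sequence. The Schedule of Events puts the survey last.
- A reader might assume an expectation effect of a few points and compute an inflated false-positive rate. Neither document gives a value for such an effect, so the result would only restate the assumption.
- A reader might think that sharing findings after the 4-month assessments would be harmless. It would still conflict with SAP 4.3 and would expose the year 1 to 3 endpoints in the protocol.

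**Conclusion.** The point holds as an inconsistency in the text. Protocol 2.2, taken literally, directs something that would break the subject's blind. The one rule that prevents this is stated for the Baseline Visit and is absent from the interim, 4-month and annual sections. It should be corrected because the blind at risk is the only masking to arm that the trial states.

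The size of any bias cannot be computed from the documents. A reader might infer that PKG+ subjects were in fact unblinded, but nothing in either document shows this. Investigators may well have applied the 4.4 rule at every visit.

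The conclusion rests on two readings: that the findings in 2.2 are PKG findings, which the preceding sentence supports, and that a subject taken through those findings could infer the arm, which follows from the report being for one arm only.

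**What to change.** - In Protocol 2.2, strike the phrase about reviewing findings with the patient, or make it expressly subject to the restriction in 4.4.
- In Protocol 4.5, 4.6 and 4.7, repeat the rule against direct reference to the PKG, for as long as SAP 4.3 keeps subjects blinded.
- For visits already completed, ask sites whether PKG findings were shared with PKG+ subjects and record the answer. If they were, do not describe the PDQ-39 and other patient-reported results as blinded in the report.

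The first two items are wording changes and need no added visits or staff. If the visit windows held, they come too late for the 4-month data, and the third item is the one that matters for the primary analysis. It costs one query to each site and a sentence in the report.
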